7.1 DEMOGRAPHIC AND OTHER BASELINE CHARACTERISTICS

Only descriptive statistics are planned for this section of the report. A table in the CTR will present the number of patients screened, randomised and treated. The number of patients prematurely discontinuing their study treatment will be shown with the reasons for discontinuation. The number and percent of patients completing the end of treatment visit and the number of patients with treatment ongoing will also be presented. Please note there will be ongoing patients at the time of the data cut-off for the primary analysis; at the time point when the final analysis will take place there will not be any more ongoing patients in this trial. Where percentages are shown, the denominator will be the number of patients treated in each treatment group.

Descriptive statistics as well as frequency counts will be provided for all demographic and baseline characteristics depicted in [Section 5.4.1](#). The CTR tables will show the relevant descriptive statistics (number and percent within categories; other descriptive statistics for continuous variables) by treatment arm.

7.4 PRIMARY ENDPOINT(S)

The primary endpoints are the PK endpoint $AUC_{\tau,ss}$ based on sampling at steady state (at week 2 and week 26) and the safety-endpoint N (%) of patients with treatment-emergent adverse events at week 24.

7.4.1 Primary analysis of the primary endpoint(s)

7.4.1.1 PK endpoint

$AUC_{\tau,ss}$ based on sampling at steady state will be calculated as specified in the CTP Sections 7.2.1 and 7.2.2. For patients receiving nintedanib in Part A, PK profiles on week 2 and week 26 are planned to be collected. For the primary endpoint $AUC_{\tau,ss}$ the $AUC_{\tau,ss}$ at week 2 will be used. If the week 2 value is missing, then it will be replaced by available $AUC_{\tau,ss}$ at week 26 (or later, if PK visit was postponed). For patients receiving placebo in Part A and nintedanib in Part B, $AUC_{\tau,ss}$ evaluated based on PK profiles at week 26 (or later, if PK visit was postponed) will be used as primary endpoint (which corresponds to week 2 on active treatment). See also [Section 6.6.1](#).

To account for potential dose reductions, $AUC_{\tau,ss}$ will be dose normalized by the actual dose taken by the patient corresponding to that PK sampling. The dose normalized $AUC_{\tau,ss}$ for nintedanib (AUC_{τ,ss_D}) will be summarised descriptively.

[figure not shown]
$AUC_{\tau,ss}$ will additionally be derived using population PK modelling (for all patients with at least one valid PK sample). Details of the analysis will be reported separately in the popPKPD report, but the main $AUC_{\tau,ss}$ results also will be included in the CTR.

The 95% CI of nintedanib CL/F_{ss} will be calculated according to company standards.

All PK analyses will be based on the pharmacokinetic analysis set (PKS), see [Section 6.3](#).

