4.1.2 Selection of doses in the trial and dose modifications

In order to match the systemic exposure reached in adult IPF patients, the nintedanib doses in paediatric patients were predicted based on body weight dependent allometric scaling (scaling of adult clearance using an exponent of 0.75, consistent with the exponent estimated in population pharmacokinetics [PopPK] analyses in adults; refer to the current version of the Investigator's Brochure Nintedanib in Idiopathic Pulmonary Fibrosis, Systemic Sclerosis and Progressive Fibrosing Interstitial Lung Disease [[c01783972-16](#)] for details). This approach is considered acceptable, assuming a minor role of developmental changes referring to nintedanib PK for the selected target population. A population mean nintedanib exposure of 80% to 125% compared to adult IPF patients treated with 150 mg b.i.d. was targeted for the determination of the planned doses by body weight bin in the paediatric population as provided in [Table 4.1.2: 1](#).

The patient's weight will be measured at screening, at randomization and at each IMP dispensing visit thereafter (see [Flow Chart](#) for details). At randomization the dose assigned will be based on the patient's weight at baseline (Visit 2). At subsequent visits the dose will be adjusted for any changes of the patient's weight resulting in a change of the body weight bin. IRT will assign the proper dose based on the patient's weight recorded at the respective visit.

Table 4.1.2: 1 Dose assignment and dose reduction possibilities based on body weight bins according to ICH E11

| Body weight bin | Weight range | Dose (b.i.d.) | Capsule strengths | Dose reduction possibility (b.i.d.) | Capsule strengths |
|-----------------|-------------------|---------------|---------------------------|-------------------------------------|---------------------------|
| 1 | 13.5* to <23.0 kg | 50 mg | 25 mg (2x) | 25 mg | 25 mg (1x) |
| 2 | 23.0 to <33.5 kg | 75 mg | 25 mg (3x) | 50 mg | 25 mg (2x) |
| 3 | 33.5 to <57.5 kg | 100 mg | 100 mg (1x) or 25 mg (4x) | 75 mg | 25 mg (3x) |
| 4 | ≥57.5 kg | 150 mg | 150 mg (1x) or 25 mg (6x) | 100 mg | 100 mg (1x) or 25 mg (4x) |

* Patients <13.5 kg of weight are excluded from the trial

Based on population anthropometric measures of weight by age, most children younger than 10 are expected to fall into body weight bin 1–2, younger adolescents in bin 3 and older ones in bin 4.

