7.5 DETERMINATION OF SAMPLE SIZE

For the primary evaluation of PK including the assessment on whether nintedanib exposure at steady-state ($AUC_{\tau,ss}$) in paediatric patients is comparable to adult exposure, the clearance

parameter needs to be estimated with adequate precision. Assuming a coefficient of variation (CV) of 70.8% (based on geometric CV [gCV] of apparent clearance at steady-state [CL/F_{ss}] after extravascular administration observed in the PK meta-analysis [[U11-1639-01](#)]), at least 20 actively treated patients with available PK measurements per age group (6 - <12 years; 12 - <18 years) would be needed to achieve at least 80% probability (loosely referred to as power in this context [[R12-0884](#)]) of having the 95% CI of nintedanib CL/F_{ss} and with this AUC_{τ,ss} within 60% and 140% of the geometric mean estimate. This calculation was performed as described by Wang et al. [[R12-0884](#)] using R Version 3.5.1.

[Table 7.5: 1](#) provides an overview of the achievable probability of having the 95% CI of nintedanib CL/F_{ss} and with this AUC_{τ,ss} within 60% and 140% of the geometric mean estimate.

Table 7.5: 1 Probability that can be expected of having the 95% CI of nintedanib CL/F_{ss} and with this AUC_{τ,ss} within 60% and 140% of the geometric mean estimate.

| gCV [%] | Sample Size | Probability [%] |
|---------|-------------|-----------------|
| 60 | 16 | 80.60 |
| 60 | 18 | 91.20 |
| 60 | 20 | 96.82 |
| 60 | 22 | 99.10 |
| 60 | 24 | 99.81 |
| 70.8 | 16 | 52.82 |
| 70.8 | 18 | 68.03 |
| 70.8 | 20 | 81.03 |
| 70.8 | 22 | 90.32 |
| 70.8 | 24 | 95.82 |
| 80 | 16 | 32.78 |
| 80 | 18 | 45.71 |
| 80 | 20 | 59.64 |
| 80 | 22 | 72.81 |
| 80 | 24 | 83.63 |

Based on the inclusion criteria of the proposed study and preliminary feasibility assessment, it is anticipated that the study will only be powered for patients with ≥ 12 years of age. PK parameters in children < 12 years will be collected and analysed but are expected to be limited due to expected small number of patients falling in that age range.

To further optimise PK assessment from the study population, on-treatment PK sampling is planned in those assigned to placebo after switching to active treatment. By this, 30 randomized paediatric patients have the possibility to contribute for the PK assessment at the time of primary analysis. This increases the sample size for the PK analysis.

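### Dividing AUCτ,ss by the mg dose corrects for dose reductions but brings back the body-weight effect that the dose bands remove; scaling to the assigned weight-band dose would do only the first

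*SAP*

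**What the plan says.** **Endpoint.** SAP 5.1 and 7.4 define the primary PK endpoint as AUCτ,ss, without normalisation. SAP 7.4.1.1 calculates it by reference to Protocol 7.2.1 and 7.2.2. Those sections give descriptive statistics for AUCτ,ss and for all PK parameters, including geometric mean and geometric CV.

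**Normalisation.** SAP 7.4.1.1 then adds, with the stated purpose "To account for potential dose reductions", that AUCτ,ss "will be dose normalized by the actual dose taken by the patient corresponding to that PK sampling". The result, AUCτ,ss_D, is to be described. The same section puts the main population-PK AUCτ,ss results in the trial report and plans a 95% CI for CL/Fss.

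**Purpose.** Protocol 7.5 says the primary PK evaluation includes whether steady-state exposure "in paediatric patients is comparable to adult exposure". Protocol 4.1.2 explains how the doses were chosen: "A population mean nintedanib exposure of 80% to 125% compared to adult IPF patients treated with 150 mg b.i.d. was targeted", by "scaling of adult clearance using an exponent of 0.75".

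**Doses.** Table 4.1.2:1 assigns 50, 75, 100 and 150 mg b.i.d. to the four weight bins. The permitted reductions are to 25, 50, 75 and 100 mg b.i.d.

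**The concern.** The weight bands exist so that a small child on a small dose has about the same AUC as an adult on 150 mg b.i.d. Dividing by the mg dose undoes this: the small child's AUC is divided by a small number and the adult's by a large one. The normalisation is meant to remove the effect of dose reductions, but it removes the weight-band adjustment as well.

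This is the primary PK endpoint and it supports paediatric dosing. If AUCτ,ss_D were set beside adult values, correctly dosed children in the lowest bin would look nearly three times over-exposed.

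**Working it through.** **Inputs from the documents.** Exponent 0.75 and target range 80% to 125% (Protocol 4.1.2); weight bins, assigned doses and reduced doses (Table 4.1.2:1); gCV of CL/Fss 70.8%, n = 20, limits 60% and 140% (Protocol 7.5).

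**Assumptions, not in the documents.** Adult reference weight 70 to 80 kg; top weight of bin 4 taken as 80 kg.

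**1. The plan's own precision figure.** σ² = ln(1 + 0.708²) = 0.4063, t(0.975; 19) = 2.093 and ln 1.4 = 0.3365. Then P[χ²(19) ≤ 19 × 20 × 0.3365² / (2.093² × 0.4063)] = P[χ²(19) ≤ 24.17] = 81.03%. This matches Table 7.5:1, and the other 14 cells also reproduce to two decimals. The calculation is made on CL/Fss.

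**2. What AUC per mg measures.** AUC = dose / (CL/F), so AUC / dose = 1/(CL/F). With CL/F proportional to W^0.75:

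- AUC per mg relative to adult = (Wref/W)^0.75
- AUC at the assigned dose relative to adult = (dose/150) × (Wref/W)^0.75

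**3. Size, with no assumed adult weight.** Between 13.5 and 57.5 kg, AUC per mg differs by (57.5/13.5)^0.75 = 4.259^0.75 = 2.96-fold.

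**4. Relative to adults, at the geometric midpoint of each bin** (range is for Wref 70 to 80 kg):

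| Bin | Assigned dose (mg b.i.d.) | AUC per mg / adult | AUC at assigned dose / adult |
|---|---|---|---|
| 1 | 50 | 2.8–3.1 | 0.94–1.04 |
| 2 | 75 | 2.0–2.2 | 1.00–1.11 |
| 3 | 100 | 1.4–1.6 | 0.95–1.05 |
| 4 | 150 | 1.0–1.1 | 1.02–1.13 |

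At the bin midpoints, AUC at the assigned dose lies inside 80% to 125% throughout, so on this model the bands do what the protocol intends. At the bin edges it runs from 0.77 to 1.16 (70 kg) or 0.85 to 1.28 (80 kg).

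**5. Pooled over patients.** Assume one third children and two thirds adolescents, with weights log-uniform over three trial ranges (for example 16–40 kg and 35–75 kg). The pooled geometric mean AUC per mg is then 1.51 to 1.67 times adult. AUC at the assigned dose is 0.94 to 1.07 times adult.

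**6. What un-normalised AUC retains.** Reduced dose / assigned dose is 25/50 = 0.50, 50/75 = 0.67, 75/100 = 0.75 and 100/150 = 0.67 in bins 1 to 4. Under dose proportionality, a reduced-dose profile shows 50% to 75% of the AUC at the assigned dose.

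**7. The three summaries for one child of 18 kg** (assigned 50 mg, reduced to 25 mg; Wref 70 kg, 80 kg in brackets):

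- AUC per mg: (70/18)^0.75 = 2.77 (3.06) times adult, at either dose.
- Un-normalised AUC on 25 mg: (25/150) × 2.77 = 0.46 (0.51).
- AUC × (50/25): 0.92 (1.02), the same as this child would show on 50 mg.

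Only the last is free of both the dose reduction and the weight effect.

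**The case against.** **The endpoint has not been replaced.** Un-normalised AUCτ,ss remains the defined endpoint, is described through the cross-reference to Protocol 7.2.1 and 7.2.2, and is also reported from the population-PK model. AUCτ,ss_D is an addition, and as the reciprocal of CL/Fss it is a legitimate summary of clearance. This stands. A reader might infer that the plan as a whole cannot show whether exposure at the assigned dose matches adults; these provisions do not support that.

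**Reductions may matter little in un-normalised AUC.** The primary value is normally taken about two weeks after active drug starts, so few patients may have been reduced by then. If 10% of profiles were on a reduced dose (assumed), the pooled geometric mean would change by a factor of 0.50^0.10 = 0.93 to 0.75^0.10 = 0.97; at 20%, 0.87 to 0.94. This also stands: the distortion is much smaller than that of AUC per mg. It is not zero, since a missing week 2 value may be replaced from week 26 or later, and the SAP itself thought an adjustment necessary.

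**The 80% to 125% range is a dose-selection target.** It is not an analysis criterion, and no visible text says AUCτ,ss_D will be held against it or against adults. This is correct, so the harm is a misreading that the plan does not yet rule out, not one it prescribes.

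**The public text is incomplete.** Content is missing directly after the AUCτ,ss_D sentence, and the body of SAP 7.4.2.1 is not shown. Protocol 7.2.2 leaves subgroup analyses to the SAP. A reader might infer that no summary by weight bin, by age group or against adults is planned; that cannot be asserted.

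**Conclusion.** The point holds as a cheap improvement. AUCτ,ss_D removes dose reductions but restores the weight effect, 2.96-fold from 13.5 to 57.5 kg under the protocol's exponent. It should be read as clearance, not as exposure at the weight-band dose. Un-normalised and population-PK AUCτ,ss can largely address exposure, with un-normalised AUC retaining any profiles at 50% to 75% of the assigned dose.

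The direction of the effect and the 2.96-fold figure need only the 0.75 exponent and the bin limits. The ratios to adults also need the assumed 70 to 80 kg reference, and the pooled ratios the assumed weight mix.

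A reader might also infer that normalising weakens the 81.03% precision in Table 7.5:1. The documents do not support this. The trial was sized on CL/Fss, whose log-scale SD is identical to that of AUC per mg whatever this SAP paragraph says. Nor do the documents say whether the 70.8% already includes variation due to weight.

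**What to change.** In SAP 7.4.1.1, keep the summary of un-normalised AUCτ,ss and define the dose-reduction-adjusted summary as

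AUCτ,ss × (dose assigned for the weight band / dose actually taken at that PK sampling).

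Take the assigned dose as the one given by Table 4.1.2:1 for the weight at the last dispensing visit before the profile. Report the geometric mean and 95% CI by age group and, where numbers allow, by weight bin. Set these against a stated adult 150 mg b.i.d. reference value with its source. Flag profiles taken on a reduced dose. Keep AUCτ,ss_D, labelled as a supportive summary of clearance. If the unpublished SAP text already contains such tabulations, only the scaling needs to change.

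The cost is one SAP paragraph and one table. The actual dose is already needed for AUCτ,ss_D, and SAP 5.4.3 already distinguishes the dose assigned by weight from a reduced dose. Dose proportionality between the reduced and assigned dose is assumed, as the SAP's normalisation already does. No dose or treatment rule changes.

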7.4.1.2 Safety endpoint

Only descriptive analyses will be performed. The number and frequency of patients with treatment-emergent adverse events by primary system organ class (SOC) and preferred term (PT) during the double-blind period, as described in [Section 7.8.1](#), will be displayed.

7.5 SECONDARY ENDPOINT(S)

Please note that any p-value presented will be considered nominal in nature and no adjustment for multiplicity will be made.

7.5.1 Key secondary endpoint(s)

This section is not applicable as no key secondary endpoint has been specified in the protocol.

7.5.2 (Other) Secondary endpoint(s)

7.5.2.1 Continuous (change from baseline) endpoints

The continuous secondary endpoint analysis will be based on the TS (according to randomised treatment), using available data from all visits (after time-windowing) from Part A and Part B and the estimate and contrast between treatments at the applicable endpoint visits will be used.

The analysis of continuous secondary endpoints is a restricted maximum likelihood (REML) based approach using a Mixed effect Model for Repeated Measures (MMRM). The analysis will include the fixed, categorical effects of treatment at each visit, age-group and the fixed continuous effects of baseline at each visit. Visit will be treated as the repeated measure with an unstructured covariance structure used to model the within-patient measurements.

Patients will be analyzed according to the age group stratum to which they belong to based on the data entered in the eCRF, which may not necessarily coincide with data used for randomisation.

The Kenward-Roger approximation will be used to estimate denominator degrees of freedom and adjust standard errors. Significance tests will be based on least-squares means (two-sided 95% confidence intervals will be presented). The primary treatment comparison will be the contrast between treatments at the endpoint visit.

In the event of non-convergence, the following methods will be attempted (in order) to overcome it:

1. Add the ‘singular=1e-10’ option in the model statement – This raises the threshold at which columns are declared linearly dependent (from typically 1e-12).
2. Set ‘maxiter=100’ in the Proc Mixed statement – This increases the number of convergence iterations used from a default of 50.
3. Set ‘scoring=4’ to specify use of the Fisher scoring algorithm in the first 4 iterations.
4. Exclude all visits > 24 weeks and report weeks > 24 data only descriptively (ANOVA) using observed data.
5. Include the statement ‘performance nothread’ – this removes multi-threading from the calculations.
6. Provide starting values for covariance parameters using a ‘parms’ statement. Estimates will be obtained from using a simpler covariance matrix.
7. Should none of the previous methods work, the covariance matrix will be changed from unstructured to Toeplitz with heterogeneous variances (TOEPH). Should this also not converge, a standard Toeplitz matrix (TOEP) will be fitted. Finally, if convergence still does not occur, then an order-1 autoregressive matrix (AR(1)) will be fitted.

[figure not shown]
Additionally, a descriptive analysis for all time points will be done.

[figure not shown]
[figure not shown]

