2.1.3 Secondary endpoints

[figure not shown]
Secondary endpoints:

- N (%) of patients with treatment-emergent pathological findings of epiphyseal growth plate on imaging at week 24, and week 52*;
- N (%) of patients with treatment-emergent pathological findings on dental examination or imaging at week 24, and week 52*;
- N (%) of patients with treatment-emergent adverse events over the whole trial;
- Change in height, sitting height, leg length from baseline at week 24, week 52*, week 76*, and week 100*.
- Change in Forced Vital Capacity (FVC) % predicted from baseline at week 24, and week 52*;
- Absolute change from baseline in Pediatric Quality of Life Questionnaire™ (PedsQL™) at week 24, and week 52*;
- Change in oxygen saturation (SpO₂) on room air at rest from baseline at week 24, and week 52*;
- Change in 6-min walk distance from baseline at week 24, and week 52*;
- Patient acceptability based on the size of capsules at week 24;
- Patient acceptability based on the number of capsules at week 24;
- Time to first respiratory-related hospitalization over the whole trial;
- Time to first acute Interstitial Lung Disease (ILD) exacerbation or death over the whole trial;
- Time to death over the whole trial.

*52 weeks, 76 weeks, 100 weeks time point will not be available for all patients.

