7.2.3 Secondary endpoint analyses

Analysis of secondary endpoints listed in [Section 2.1.3](#) will be descriptive in nature using a mixed model with repeated measurements (MMRM) for continuous endpoints. Time-to-event endpoints will be displayed descriptively using the Kaplan-Meier method. Categorical endpoints, safety and tolerability will be displayed descriptively in frequency tables. Further details will be provided in the TSAP.

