Start day	End day (included)	Length of the time-window [days]	Visit number	Visit name	Planned day of the visit
-84	1	85	2	Baseline	1
2	29	28	3	2 weeks	15
30	64	35	4	6 weeks	43
65	127	63	5	12 weeks	85
128	176	49	6	24 weeks	169
177	218	42	7	26 weeks	183
219	309	84	8	36 weeks	253
310	407	112	9 (p)	52 weeks	365 (V _p)
(V _p + 1) + (V _{p+1} - V _p)/2	V _{p+1} + (V _{p+2} - V _{p+1})/2	(V _{p+2} - V _p)/2	p+1		V _{p+1} = V _p + 12 x 7
...	Every 12 weeks thereafter	...

V_p denotes the planned day of the visit

^[1] First trial drug intake date is taken into account as reference to calculate time windows

^[2] Only for LDH biomarker analyses: Biomarker values are only considered up to + 7 days after last drug intake.

Table 6.7: 2 Time windowing rules for weight

Time window of actual day ^[1]			Allocated to		
Start day	End day (included)	Length of the time-window [days]	Visit number	Visit name	Planned day of the visit
-84	1	85	2	Baseline	1
2	29	28	3	2 weeks	15
30	64	35	4	6 weeks	43
65	127	63	5	12 weeks	85
128	211	84	6	24 weeks	169
212	309	84	8	36 weeks	253
310	407	112	9 (p)	52 weeks	365 (V _p)
(V _p + 1) + (V _{p+1} - V _p)/2	V _{p+1} + (V _{p+2} - V _{p+1})/2	(V _{p+2} - V _p)/2	p+1		V _{p+1} = V _p + 12 x 7
...	Every 12 weeks thereafter	...

V_p denotes the planned day of the visit

^[1] First trial drug intake date is taken into account as reference to calculate time windows

Table 6.7: 3 Time windowing rules for height and leg length

Time window of actual day ^[1]			Allocated to		
Start day	End day (included)	Length of the time-window [days]	Visit number	Visit name	Planned day of the visit
-84	1	85	2	Baseline	1
2	127	126	5	12 weeks	85
128	211	84	6	24 weeks	169
212	309	98	8	36 weeks	253
310	449	140	9 (p)	52 weeks	365 (V _p)
(V _p + 1) + (V _{p+1} - V _p)/2	V _{p+1} + (V _{p+2} - V _{p+1})/2	(V _{p+2} - V _p)/2	p+1		V _{p+1} = V _p + 24 x 7
...	Every 24 weeks thereafter	...

V_p denotes the planned day of the visit

^[1] First trial drug intake date is taken into account as reference to calculate time windows

Table 6.7: 4 Time windowing rules for dental examination and bone imaging

Time window of actual day ^[1]			Allocated to		
Start day	End day (included)	Length of the time-window [days]	Visit number	Visit name	Planned day of the visit
-84	15	99	2	Baseline ^[2]	1
16	127	112	5	12 weeks	85
128	211	84	6	24 weeks	169
212	309	98	8	36 weeks	253
310	449	140	9	52 weeks	365 (V_p)
450	617	168	11 (p)	76 weeks	533

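### The MMRM for FVC % predicted and SpO2 has no stated last visit: sparse visits after week 52 make it non-estimable, and fallback step 4 then drops the estimable week-52 endpoint

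*SAP*

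**What the plan says.** SAP 7.5.2.1 fits one REML model per continuous secondary endpoint "using available data from all visits (after time-windowing) from Part A and Part B and the estimate and contrast between treatments". The same sentence limits the reported contrasts to the visits at which an endpoint is defined. The fixed effects are treatment by visit, baseline by visit and age group. On the covariance it says: "Visit will be treated as the repeated measure with an unstructured covariance structure used to model the within-patient measurements".

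The windows for FVC and SpO2 (SAP 6.7, Table 6.7: 1) run through weeks 2, 6, 12, 24, 26, 36 and 52 and then "Every 12 weeks thereafter". Those for height and leg length (Table 6.7: 3) continue "Every 24 weeks thereafter". The endpoints stop earlier. Protocol 2.1.3 lists "Change in Forced Vital Capacity (FVC) % predicted from baseline at week 24, and week 52", the same two time points for SpO2, and for growth "Change in height, sitting height, leg length from baseline at week 24, week 52*, week 76*, and week 100".

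If the model does not converge, SAP 7.5.2.1 gives an ordered list of remedies. Steps 1 to 3 change numerical settings. Step 4 is: "Exclude all visits > 24 weeks and report weeks > 24 data only descriptively (ANOVA) using observed data". Simpler covariance structures come only at step 7. SAP section 7 repeats every analysis of the first lock (DBL1) at the second (DBL2). Protocol 7.2.3 describes the secondary analyses as "descriptive in nature using a mixed model with repeated measurements (MMRM) for continuous endpoints".

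**The concern.** The phrase about applicable endpoint visits limits which contrasts are reported. It does not limit which visits enter the model. With staggered entry and a lock on a calendar date, the latest 12-week window always holds only the few earliest patients, yet each added visit brings a full row of covariance parameters. For FVC and SpO2 the visits after week 52 carry no endpoint but can make the whole model non-estimable.

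The remedies then act in an unhelpful order. Numerical settings cannot supply missing patients, and step 4 cuts back to week 24, so week 52 leaves the model although the data support it. The planned likelihood-based analysis, which uses the earlier visits of patients who have not reached week 52, would be replaced by an ANOVA of observed values for an avoidable reason.

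**Working it through.** **Inputs.** Protocol 3.2 projects 18 months' recruitment (78 weeks) for the minimum 30 patients and at least 26 weeks' treatment. Allocation is 2:1. Assumed, because the documents do not give them: uniform accrual, no dropout, and DBL2 13 to 52 weeks after DBL1.

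**Check against the plan's own figure.** Maximum follow-up at DBL1 is 78 + 26 = 104 weeks and the mean is (26 + 104)/2 = 65 weeks. Placebo patients lose 24 weeks of nintedanib exposure, leaving 41. Mean nintedanib exposure is (2 × 65 + 41)/3 = 57 weeks, or 13.1 months. Protocol 3.2 says about 12 months, with early patients beyond two years. The projection is reproduced closely enough to use.

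**Patients needed.** With near-monotone follow-up, the k-th post-baseline visit is regressed on the k − 1 earlier visits, two arm means and a baseline slope, and needs one residual degree of freedom: (k − 1) + 2 + 1 + 1 = k + 3 patients (shared age effect ignored). Week 52 is visit 7.

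**Patients expected at DBL1.** n(w) = 30 × (104 − w)/78. The last column is the share of 20,000 simulated accruals in which a model ending at that week meets the requirement at every visit.

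| Last visit (week) | k | Needed | Expected n | Estimable |
|---|---|---|---|---|
| 52 | 7 | 10 | 20.0 | 100% |
| 64 | 8 | 11 | 15.4 | 96% |
| 76 | 9 | 12 | 10.8 | 38% |
| 88 | 10 | 13 | 6.2 | 0.3% |
| 100 | 11 | 14 | 1.5 | 0% |

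With visits to week 100 there are 11 × 12/2 = 66 covariance parameters; to week 52 there are 7 × 8/2 = 28.

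**Waiting for DBL2 does not help.** Later follow-up fills the old windows and opens new sparse ones. Expected n at the last planned visit, against the number needed:

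- +13 weeks: week 112, 30 × 5/78 = 1.9 against 15
- +26 weeks: week 124, 30 × 6/78 = 2.3 against 16
- +39 weeks: week 136, 30 × 7/78 = 2.7 against 17
- +52 weeks: week 148, 30 × 8/78 = 3.1 against 18

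The model with all visits was estimable in 0% of simulated accruals at each lag, and the one ending at week 52 in 100%. In general, at 30 patients per 78 weeks the last 12-week window holds on average at most 12 × 30/78 = 4.6 patients. Varying N from 30 to 50, recruitment from 12 to 30 months and the lag from 0 to 52 weeks left a failing tail in every case.

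**Direct fits.** The SAP model was fitted by REML to simulated trials with assumed 10% yearly dropout and 3% missed visits. A fit was called singular if the smallest eigenvalue of the fitted correlation matrix was below 1e-6. With all visits, 34 of 35 fits were singular at DBL1 and 21 of 21 at DBL2 (+26 weeks). Ending at week 52, 1 of 60 and 0 of 60 were.

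**Growth endpoints.** Week 100 is the sixth post-baseline visit in Table 6.7: 3, so it needs 9 patients. At DBL1 about 1.5 are expected by planned visit. At DBL2 +26 weeks there are 30 × 30/78 = 11.5, but week 124 has 2.3 against 10. At +13 weeks the planned-visit count for week 100 is 30 × 17/78 = 6.5. If end-of-treatment values are windowed by actual day, the week-100 window opens at day 618 (88.1 weeks) and the count becomes 30 × (117 − 88.1)/78 = 11.1. The answer turns on the lag and on that windowing.

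**The case against.** Three points against the concern have force.

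**Trigger.** The remedies start only on non-convergence. The counts and fits show a singular covariance, which software can report as converged. A reader might infer that step 4 is certain to remove week 52; the documents do not support that. But the other path is no better: the remedies never start, and an unreliable fit may be reported.

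**Visibility.** Parts of SAP 7.5.2.1 after the list of remedies are not shown in the public copy, so a last visit stated there cannot be excluded. The claim is that none appears in the visible text, which refers to all visits.

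**Consequence.** Protocol 7.1 plans no confirmatory testing and SAP 7.5 calls p-values nominal. Week 24, the placebo-controlled contrast, stays in the model. Week 52 is still reported by ANOVA and descriptively, and by then everyone is due to be on open-label nintedanib, so it compares early with delayed start. All of this stands and limits the severity.

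A reader might also infer that the long-term growth endpoints will be lost with a calculable probability. No DBL2 interval is given, and the number of incorrectly measured sitting heights to be excluded (SAP 5.2.2.4) is unknown, so no exact probability can be supported. PedsQL and 6MWT have only two post-baseline windows and are not affected.

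**Conclusion.** The point holds for FVC % predicted and SpO2. As visibly written, their model includes visits that carry no endpoint and that make it almost never estimable at either lock, while a model ending at week 52 has about twice the patients it needs at DBL1 (20 against 10). This rests on the protocol's recruitment projection with uniform accrual. Recruitment within about six months would leave no visits after week 52 at DBL1, but that is not what the protocol assumes. For growth, visits after week 100 add the same kind of sparse tail at DBL2; how often a model to week 100 would itself be estimable is left open.

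Severity is minor. The primary endpoints are untouched, and the gain is a cheap one: keeping the planned method for an endpoint that the data can support.

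**What to change.** 1. End the FVC % predicted and SpO2 models at week 52 (weeks 2, 6, 12, 24, 26, 36, 52) at both locks, and report later visits descriptively.
2. Reword step 4 so that it first excludes visits after the variable's last endpoint visit (week 52 for FVC and SpO2; week 100 for height, sitting height and leg length), and only then all visits after week 24.
3. Extend the trigger for the remedies to a non-positive-definite Hessian or a singular covariance estimate.

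The cost is a few sentences in the SAP. The protocol's MMRM is kept. The downside is that sparse visits after the last endpoint no longer inform the model.
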